1.3 Research Design and Methods

A. Order of occurrence of research procedures

The research procedure involves use of the nerve stimulator technology of the blockade monitor

The study is designed to compare the effectiveness of using a nerve stimulator in conjunction with ultrasound guidance when performing a supraclavicular block. Nerve stimulators have been used for

many years in the performance of various peripheral nerve blocks. With the advent of ultrasound technology, a majority of practitioners have abandoned the use of nerve stimulators and perform these blocks with the ultrasound as the only method of confirming needle location. There have not been many studies to compare the onset, quality, or duration of ultrasound guided supraclavicular blocks with or without the use of a nerve stimulator.

We propose a randomized study design, based on two groups (standard and test treatments). All patients between the ages of 21 and 89 that can communicate in English and meet the selection criteria that are scheduled for upper extremity surgery are eligible to participate.

After consenting to the study, the patient will be randomly assigned to one of two groups, standard or test treatment.

Patients in both groups will receive:

- IV placement on the non-surgical arm with IV fluid infused at 1 ml/kg/hr
- Oxygen by nasal cannula
- Sedation with Midazolam
- Oximetry and EKG monitoring
- Ultrasound-guided supraclavicular block performed as follows:
 - After adequate IV sedation, chloroprep antiseptic solution will be applied to sterilize the injection site.
 - The Sonosite ultrasound probe will be placed in a sterile wrapping and used to identify the subclavian artery as it transverses the upper thorax in the fascia superior to the apex of the lung.
 - The skin overlying the superior aspect of the ultrasound-identified site will be anesthetized with 1% Lidocaine.
 - Through the anesthetized area, a Braun 4 x 21 Stimuplex needle (#4894260) will be inserted and using ultrasound guidance, directed to the area surrounding the subclavian artery.
- In the Standard Group, in the absence of paresthesia and after negative aspiration, the 40 ml of local anesthetic block will be administered.
- In the Test Group, the Braun DIG –R-C Stimuplex blockade monitor system will be initially set at 1 milliamp as the needle approaches this area. As the proximity of the tip of the needle to the components of the brachial plexus becomes evident by ultrasound approximation and the stimulation pattern of the hand and wrist, the output of the system will be reduced to .3-.5 millamps. In the absence of paresthesia and after negative aspiration, the 40 ml of local anesthetic block will be administered.

- Description of Braun DIG-R-C Stimuplex Blockade Monitor
This monitor is a nerve stimulator used for locating peripheral nerves in regional anesthesia and pain therapy. It is a class IIa medical device. During the performance of a regional block, as the needle tip approaches the nerve, there appears a muscle twitching in the appropriate muscle group.. This is not painful to the patient. The stimulus is adjusted to estimate the proximity of the needle to the nerve bundle. As the output of the impulse generator is turned lower, there will still be twitching at close range to the nerve. This is the ideal injection point as the device indicates that the stimulus is so low that the needle tip is not within the nerve sheath itself, but instead close to the nerve. This is one way to safely determine how close to a nerve the needle is, without entering the nerve. Only the subsequently injected medicine will enter the nerve, providing an additional element of safety.

B. Data point collection

- During the performance of the block, when the stimulation pattern is still evident at the lower output of the block monitor, the pattern of the movement of the hand will be recorded
- Patients in both groups will be assessed every 5 minutes for the quality of the block, ending at 20 minutes post block. This will involve 4 data points.
- Assessment includes (**See data collection sheet**):
 - response to strength testing of the upper extremity
 - response to hot and cold discrimination with an alcohol pad

response to fine touch provocation

Data points for all subjects will be taken during and after surgery to assess:

1. Speed of onset of the block
(At 5 min intervals, subjects will be asked to flex their arm against gravity to determine onset of the block).
2. Assessment of intraoperative quality of the block
(Beginning 5 minutes after the placement of the local anesthetic, and at 5 min intervals, subjects will be asked to distinguish hot and cold and fine touch in the dermatomes of the shoulder and hand. They will have the opportunity to express inadequacy of the block at which time they will receive additional anesthetic in the form of IV supplement or general anesthesia.
 - Duration of block
(At 30 min intervals post op, subjects will be evaluated for sensory and motor function as compared to the contralateral (opposite) arm, or compared to their preoperative evaluation. Two evaluations will be done, each taking approximately 5 minutes

C. Duration of study and length of time the participant will participate

The duration of the study will be 2 years

The study participant will be assessed during the injection and for 20 minutes after the injection for the block itself and the duration of the entire research data collection would be thirty minutes

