1.0 Research Introduction

1.1 Purpose/Specific Aims

We propose to compare the use of a nerve stimulator for ultrasound-guided supraclavicular block (test treatment) to the standard treatment where nerve stimulators are not used (standard treatment) for patients undergoing upper extremity surgery. The block is routinely performed to provide analgesia to the upper limb prior to surgery. The hypothesis is that using the nerve stimulator in conjunction with the ultrasound will provide a more accurate method of performing the supraclavicular block. This should result in better outcomes, including improved onset time of analgesia and improved pain control during and after surgery. There is no increased risk to the patients participating in the test treatment group compared to those in the standard treatment.

A. Objectives

The objectives of the study are to demonstrate a difference in quality and effectiveness of analgesia (completeness of pain relief), or extended duration of block as a result of the addition of a nerve stimulator in the performance of the block.

B. Hypotheses / Research Question(s)

The hypothesis is that using a nerve stimulator will improve the effectiveness, quality, and outcome of ultrasound guided supraclavicular blocks.

1.2 Research Significance (*Briefly describe the following in 500 words or less*):

Supraclavicular (above the collarbone) block is a popular anesthetic technique for upper extremity surgery. Historically, this technique utilized anatomically guided needle placement for proper distribution of the anesthetic, but it carried the risk, among others, of pneumothorax. This risk was significantly reduced by the use of ultrasound guidance for needle placement. We propose to further improve the efficacy of this now standard regional block technique by using a nerve stimulator in addition to ultrasound visualization.

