1.6 Study Variables

A. Independent Variables, Interventions, or Predictor Variables

The only difference (the intervention) between the study groups involves the use of the nerve monitor during the performance of the block

The performance of the block with both the ultrasound and the nerve monitor is in excess of the standard of care which utilizes the ultrasound alone , but the needle used for the block is the same in both groups. It is the Stimuplex Teflon coated needle which can be used with or without application of the nerve monitor function

B. Dependent Variables or Outcome Measures

I have expectations that the use of the nerve block monitor will result in a faster speed of onset of the block as the performance characteristics of the block placement relative to the target nerve may be improved.

Dependent variable would be success of the block as measured objectively by speed of onset.

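### Block checks stop at 20 minutes, the planned control mean, and the supplied text gives no rule for scoring patients without onset by then; scoring them 20, scoring them 25 or dropping them each estimates less than the planned 7 minutes

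*Protocol*

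**What the plan says.** Protocol 1.3 B sets the block checks: "Patients in both groups will be assessed every 5 minutes for the quality of the block, ending at 20 minutes post block". It adds: "This will involve 4 data points". Section 1.3 C repeats the limit: "The study participant will be assessed during the injection and for 20 minutes after the injection for the block itself".

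The onset item in 1.3 B reads: "At 5 min intervals, subjects will be asked to flex their arm against gravity to determine onset of the block". It gives no end time, and its list is introduced by "Data points for all subjects will be taken during and after surgery to assess". During the block checks patients can report that the block is inadequate: "They will have the opportunity to express inadequacy of the block at which time they will receive additional anesthetic".

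Section 1.6 B names the outcome: "Dependent variable would be success of the block as measured objectively by speed of onset". Section 1.1 words the aim as "improved onset time of analgesia and improved pain control during and after surgery".

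Section 1.5 gives 34 per group for a fall in onset time from 20 to 13 minutes and sets 100 patients for qualitative data. Section 6.1 B gives SD 10 and 33 per group, and then calls 50 per group sufficient. Section 4.5 C gives 64 as the total required. The only tests named are t-tests and ANOVA (6.1 A), and they are not tied to an outcome. SAP 9.4 (missing data), 10.2 (derived variables) and 11.1 (primary analysis) still hold template instructions.

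**The concern.** Onset is planned as a fully observed continuous time, but it is watched only until 20 minutes, when many control patients are expected not to have reached it. Those patients have no onset time to enter in a t-test. Someone must decide whether to give them 20, give them a later value, censor them or leave them out, and each choice estimates a different quantity. The default in most software, leaving out a blank, selects patients on the outcome itself and does so more in the control arm.

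Two things are at stake. A result of 3 to 4 minutes could be read as falling short of the planned 7 when it is what the plan's own figures predict. And a rule settled after the data are seen leaves the main result open to choice.

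**Working it through.** **Inputs.** Means 20 (control) and 13 (test), from 1.5; SD 10, alpha 0.05 and power 80%, from 6.1 B; checks at 5, 10, 15 and 20 minutes, from 1.3 B. The shape of the onset distribution is not in the documents; normal (negative times floored at 0), gamma and lognormal are assumed in turn.

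**The plan's own figure.** n = 2 × [(1.960 + 0.842) / (7/10)]² = 32.04, so 33 per group; the noncentral-t version gives 33.02, so 34. Both stated sizes reproduce, two-sided, for onset times that are never cut off.

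**A bound that needs no distribution.** If no score exceeds 20, a control mean of 20 requires every control patient to score exactly 20. Scores between 5 and 20 cannot have an SD above (20 − 5)/2 = 7.5. If non-onset is scored 25, the SD at a mean of 20 cannot exceed √[(25 − 20)(20 − 5)] = 8.7. Neither rule can give mean 20 with SD 10.

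**Expected differences.** Each onset is recorded at the first check at or after it occurs. Normal case as an example:
- Control: probabilities of first record at 5, 10, 15 and 20 are 0.067, 0.092, 0.150 and 0.192, with 0.500 showing no onset. Scored 20, the mean is 17.33.
- Test: 0.212, 0.170, 0.197 and 0.179, with 0.242 showing no onset. Scored 20, the mean is 14.13.
- Scored 20: 17.33 − 14.13 = 3.20.
- Scored 25: 3.20 + 5 × (0.500 − 0.242) = 4.49.
- Dropped: (17.33 − 20 × 0.500)/0.500 − (14.13 − 20 × 0.242)/0.758 = 14.66 − 12.26 = 2.40.

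| | Normal | Gamma | Lognormal |
|---|---|---|---|
| No onset by 20, control | 50.0% | 43.3% | 40.7% |
| No onset by 20, test | 24.2% | 19.7% | 16.5% |
| Difference, scored 20 (min) | 3.20 | 4.23 | 4.34 |
| Difference, scored 25 (min) | 4.49 | 5.41 | 5.55 |
| Difference, dropped (min) | 2.40 | 3.92 | 4.07 |
| Power at 50/arm, scored 20 | 84% | 99% | >99% |
| Power at 50/arm, scored 25 | 89% | 98% | >99% |
| Power at 50/arm, dropped | 38% | 90% | 97% |
| Power at 34/arm, scored 20 | 69% | 93% | 98% |
| Power at 32/arm, scored 20 | 66% | 92% | 97% |

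Power is from 20,000 simulated trials per case; 32 per arm is half of the 64 in section 4.5 C. Of 50 per arm, about 20-25 control and 8-12 test patients would have no recorded onset.

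**What score would return 7?** Solve (scored-20 difference) + (s − 20) × (difference in non-onset proportion) = 7. This gives s = 34.7, 31.7 and 31.0 for the three shapes, so about 31-35.

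**Type I error.** With no true difference, each single rule gives about 5%. If the most favourable of the three were picked afterwards, it would be about 8-10%.

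**Sensitivity to the cited figures.** Taking the 14 ± 6 quoted in 1.5 as control and assuming the same 35% reduction (test mean 14 × 0.65 = 9.1, SD 6), 14-16% of controls have no onset by 20 minutes. The 4.9-minute difference becomes 3.8-4.3 (scored 20), 4.4-4.8 (scored 25) or 3.25-4.1 (dropped). Power at 50 per arm is 96% or more scored 20 or 25, and 88% or more dropped.

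**The case against.** **No analysis could return 7 minutes.** A reader might infer this, but it is too strong. It holds for the three rules examined; a score of about 31-35 would return 7. Such a score would be arbitrary, which is itself a reason to settle it in advance.

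**The trial is underpowered.** A reader might infer this too. The SD shrinks along with the difference, so at 50 per arm power stays at 84% or more when non-onset is scored 20 or 25. The reassurance does not reach every size in the protocol: at 34 or 32 per arm the stated 80% is not assured. Nor can the 50 per arm be set aside as serving qualitative data only, since 6.1 B ties it to the onset calculation.

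**The low ends come from an unlikely shape.** This stands in part. The floored normal has an uncut difference of only 6.6 minutes before any stop at 20. With gamma and lognormal alone, the differences are 4.2-4.3, 5.4-5.6 and 3.9-4.1 minutes: still well below 7, but with power at 50 per arm of 98% or more (scored 20 or 25) and 90-97% (dropped).

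**Onset may be followed longer, or the rule may be on the data sheet.** The onset item has no end time of its own and sits under a heading about surgery and afterwards. However, no later onset check is described; the postoperative checks concern duration of block. The sheet was not available, so the finding is that the supplied text has no rule, not that none exists. An analysis rule still belongs in the protocol or SAP.

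**Choosing the rule afterwards is hypothetical.** Agreed. Nothing in the documents suggests that it is intended.

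**Conclusion.** The point holds as a gap in the definition of the main result and should be fixed. Under the plan's own means and SD, two-fifths to one-half of control patients would have no recorded onset. The three scoring rules considered give 2.4-5.6 minutes in place of 7, depending on the rule and the assumed shape. Dropping is the harmful choice: it removes 2 to 2.5 times as many controls as test patients and can take power at 50 per arm down to 38%.

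The conclusion rests on reading 20 minutes as the end of onset checks, on 20 minutes being the control mean as in 1.5, and on the assumed distributions. The bounds on mean and SD need no distribution. The loss is much smaller if the cited 14 ± 6 describes the control arm, but the rule would still be open.

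**What to change.** Change wording only, before analysis:

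- **Protocol 6.1 A and SAP 11.1:** settle one rule that keeps all randomised patients and never drops a patient for lack of onset. A suitable choice is to score no onset by 20 minutes as 20, keep the t-test, and call the result the difference in restricted mean recorded onset time to 20 minutes. A log-rank or discrete-time analysis censored at 20 is an acceptable alternative or sensitivity analysis.
- **Companion result:** report the percent with onset by 20 minutes per arm, with a confidence interval for the difference.
- **Extra anesthetic:** for the analysis, count patients supplemented, converted or failed before onset was seen as having no onset by 20 minutes; keep an onset time already observed.
- **Protocol 1.3:** state the onset event and its threshold, reconciling the arm-flexion test with the onset of analgesia named in 1.1 and 1.5. Reconcile the passages on when onset checks end.
- **Protocol 1.5:** say that the 34 per group applies to uncut times, and restate power for the chosen rule at 34 and 50 per arm.

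The recommended analysis uses the same four checks and the same t-test and needs no new data. The cost is a headline effect smaller than 7 minutes (3.2-4.3 under the plan's figures). An onset seen at the 20-minute check also scores the same as none, which is why the percent with onset is needed. That percent is imprecise: at 50 per arm, the 95% interval for the difference is about ±17-18 points, for example 1.96 × √(0.500 × 0.500/50 + 0.242 × 0.758/50) = 0.18.

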4.3 Subject Randomization

Subjects will be randomized into 2 treatment groups. The experimental group (n=50) will receive an ultrasound guided supraclavicular block performed with a nerve stimulator. The control group (n=50) will receive the standard treatment for an ultrasound guided supraclavicular block).

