7.3 Randomization and Blinding

(ICH E3; 9.4.3, 9.4.6. ICH E9; 2.3.1, 2.3.2)

Describe essential components of the randomization and blinding methodology and process in enough detail to enable its reproduction. Include any minimization, stratification or blocking procedures used to avoid or minimize bias. This section may be copied from the protocol but it may be necessary to include additional information details, particularly regarding block size. However, in a double-blind study it is not appropriate to include such information in the SAP but document it within the final study report, in which case document that these details will be provided in the final study report. Document any software packages used to perform the randomization and the method used for retrieving the treatment assignments.

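### Must the plan name a masked scorer for block onset, quality and duration, given that nothing bars the person who placed the block from scoring it?

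*Protocol*

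**What the plan says.** Protocol 1.3B describes three sets of checks, all in the passive voice with no scorer named.

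- **Onset:** "subjects will be asked to flex their arm against gravity to determine onset of the block", every 5 minutes up to 20 minutes after the block.
- **Quality:** "subjects will be asked to distinguish hot and cold and fine touch in the dermatomes of the shoulder and hand", on the same schedule.
- **Duration:** sensory and motor function at 30-minute intervals after surgery. "Two evaluations will be done, each taking approximately 5 minutes".

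Protocol 4.3 states that "Subjects will be randomized into 2 treatment groups" and gives the group sizes; it does not mention masking. SAP 7.3 is still the template instruction, "Describe essential components of the randomization and blinding methodology and process in enough detail to enable its reproduction", with nothing filled in. SAP 7.1 is in the same state.

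Protocol 1.6B records the expected direction ("I have expectations that the use of the nerve block monitor will result in a faster speed of onset of the block") and describes the outcome as "success of the block as measured objectively by speed of onset". Protocol 1.6A notes that "the needle used for the block is the same in both groups". Other roles are assigned: consent and capacity in 4.2, 4.6 and 4.7, data entry and analysis in 6.1. Scoring is not. The data collection sheet (Appendix A) was not among the documents available, so a scorer field there cannot be ruled out.

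**The concern.** The operator necessarily knows whether the stimulator was used. Protocol 2.1 describes the investigators as staff anesthesiologists accustomed to this block, and 4.11 has data recorded in the holding area or where the block is placed. As written, the person who placed the block may also decide at which 5-minute check it took effect. Arm flexion needs the patient's effort and the examiner's reading; hot/cold and fine touch leave more room for judgement.

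The patient may also know the arm. Section 4.9 says the steps are described beforehand, and only test-arm patients feel stimulated twitches, although midazolam in both arms may blunt this.

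A scorer who expects the stimulator to work faster could read a borderline response one check early in the test arm. Systematic error of that kind does not shrink when 100 patients are enrolled rather than 68. Section 6.1A uses the results to judge whether a larger study is supported, so a modest difference that might be scoring bias would be hard to interpret.

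**Working it through.** **1. The plan's own figure.** Inputs: 20 v 13 min (Protocol 1.5 and 6.1B), SD 10 (6.1B), alpha 0.05, power 0.80; two-sided testing is assumed.

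n per arm = 2(1.960 + 0.842)² / (7/10)² = 32.04, rounded up to 33. The t-test version gives 33.02, rounded up to 34. Both stated figures (33 in 6.1B, 34 in 1.5) reproduce. Scoring bias does not enter this calculation, and the concern proposes no new sample size.

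**2. How far misreading could move the mean.** The assumptions here are mine, not the plan's: normal onset times; each recorded as the first 5-minute check at or after onset; onset beyond 20 min coded as 25; a fraction *f* of test-arm scores read one check early; no true effect. The settings are 14 ± 6 (Protocol 1.5) and 20 ± 10 (6.1B).

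Mean shift = *f* × 5 min × share of scores that can move. A score at the 5-minute check cannot move; its share is Φ((5−14)/6) = Φ((5−20)/10) = Φ(−1.5) = 0.067 in both settings.

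- Scores beyond 20 min can be read early: share = 1 − 0.067 = 0.933 in both settings.
- They cannot: at 14 ± 6 the share beyond 20 is 0.159, leaving 0.774; at 20 ± 10 it is 0.500, leaving 0.433.

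| Setting | Shift (min) at *f* = 10 / 20 / 30% | Two-sided false-positive rate, 50 per arm |
|---|---|---|
| 14 ± 6, >20 can move | 0.47 / 0.93 / 1.40 | 6.8 / 12.6 / 22.3% |
| 14 ± 6, >20 cannot | 0.39 / 0.77 / 1.16 | 6.2 / 10.1 / 16.3% |
| 20 ± 10, >20 can move | 0.47 / 0.93 / 1.40 | 6.4 / 11.2 / 19.2% |
| 20 ± 10, >20 cannot | 0.22 / 0.43 / 0.65 | 5.2 / 6.2 / 7.6% |

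The rates come from 100,000 simulated trials per setting; a separate run of 40,000 agreed within simulation error. Coding onset beyond 20 min as 20 or 30 widens the ranges to 5.2–7.0 / 5.7–13.4 / 6.4–24.4%.

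**3. What drives the inflation.** With the same misreading fraction in both arms, rejection stays at about 5% (4.8% to 5.2% over all settings, 40,000 trials each). The excess comes entirely from assuming that only the test arm is misread.

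**4. Shift against the significance threshold.** The SD of the recorded scores is 5.68 (14 ± 6) or 6.36 (20 ± 10). The difference needed with 50 per arm is 1.984 × SD × √(2/50) = 2.25 or 2.52 min. The largest shift in the table, 1.40 min, falls short of both, and is 1.40/7 = 20% of the target. The smallest is 0.22/7 = 3%.

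**5. What masking would cost.** The scorer is needed for the 20 minutes after the block plus two checks of about 5 minutes: 20 + 2 × 5 = 30 min per patient, × 100 = 3,000 min = 50 hours. This is contact time only; waiting or returning for the post-operative checks adds to it. Protocol 4.11 places two anesthesiologists around the patient. One belongs to the block service. The other is the case attending, whom 4.7B keeps out of the performance of the study. Neither is shown to be an available, independent scorer.

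**The case for a change.** The strongest case for a change has three parts. First, the bias is systematic, so extra patients cannot cure it, and the main outcome is exactly what it would affect. Larger assumed shifts do more harm: a uniform 2.5-minute shift with 50 per arm gives 24.0% false positives at SD 10 and 54.9% at SD 6 (normal approximation). Second, masking a scorer is feasible in principle: the needle is common to both arms, and someone absent at placement need not know the arm. Third, no visit or check is added, so the least the plan could do is say who scores.

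Much of this stands. The documents are silent, operator scoring is not barred, and bias toward the test arm is plausible given the stated hypothesis. Three things do not stand.

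- **Direction is not shown.** The expectation in 1.6B is written in the first person and is not attributed to the scorers. Protocol 1.3A says most practitioners have given up stimulators, so a scorer could lean the other way.
- **Size is not known.** No document supports 10%, 20%, 30% or a 2.5-minute shift, and arm flexion is a gross sign.
- **The cheap parts do not work alone.** Splitting the data sheet, logging masking status or dropping the claim of objectivity changes no score while the scorer still knows the arm. The worry that one form reveals the arm rests on an appendix not seen.

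Residents appear as recruiters (4.2D) and fellows as analysts (6.1E), so other staff exist. Nothing shows that any of them is free for this task.

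**Conclusion.** The gap is real, but no change to the plan follows. The one measure that would remove scorer bias is in effect an extra assessor, at 50 hours or more, in a single-site study whose stated use is to decide whether a larger study is worthwhile. Going without is a fair trade-off. The remaining measures write down an omitted detail that the report can supply: who scored, whether they knew the arm, and that unmasked scoring and patient awareness are limitations.

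On the assumptions shown, the effect runs from negligible (5.2% false positives, 0.22 min) to moderate (22.3%, 1.40 min), and is nil if misreading is equal between arms. A difference near the planned 7 minutes would not be explained by shifts of this size; one near the 2.25 to 2.52 minute threshold should be read with caution. This rests on the assumed misreading fractions, normal onset times, the coding of onset beyond 20 minutes, a two-sided t-test on onset (6.1A lists t-tests without tying one to this outcome), and an unseen Appendix A. If that form names an independent scorer, the concern falls away for the scorer, though not for the patient.
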